5.7 Multiple Comparisons/Multiplicity

To control for the familywise error rate at 0.05 level in the testing of primary and selected secondary endpoints, a hierarchical testing approach will be used. The endpoints will be tested in the following order:

Global protocol	US protocol	2-Sided alpha
1. ABR in the efficacy period	1. ABR in the treatment period	0.05
2. ABR in the treatment period	2. ABR in the efficacy period	0.05
3. Annualized spontaneous bleeding rate in the efficacy period		0.05
4. Annualized joint bleeding rate in the efficacy period		0.05
5. Change in Haem-A-QOL physical health score and total score in the treatment period		0.05

If testing of any of the endpoints is not statistically significant, formal testing of subsequent endpoints will stop and the null hypothesis for subsequent tests will not be rejected. For endpoint 5, change in Haem-A-QOL physical health score in the treatment period will be tested first followed by change in Haem-A-QOL total score in the treatment period. The testing of the secondary endpoint ABR in the onset period will not be included in this hierarchical testing procedure.

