6.3.1.2 Efficacy Analysis based on Treatment Policy Strategy

A supportive efficacy analysis will be performed by including all bleeding episodes collected through the end of the study, regardless of any premature treatment discontinuation, excluding only events due to major or minor surgeries based on ITT Analysis Set as in the primary analysis. The same negative binomial model as in the primary analysis will be used. It assesses the benefits of the fitusiran treatment policy strategy relative to on-demand treatment.

A sensitivity analysis to the above treatment policy analysis will be performed by including all bleeding events (ie, not excluding bleeding events due to surgeries).

Missing data sensitivity analyses using controlled imputation

The above efficacy analysis assumes the uncollected bleeding events after study discontinuation are missing at random (MAR). Sensitivity analyses will be performed to assess the robustness of this treatment policy analysis by imputing the missing data based on different missing data mechanism. The missing data will be imputed using multiple imputation (MI) methods for recurrent event data based on pattern mixture models (Keene et al, 2014) to assess the impact of different assumptions about the statistical behavior of post-withdrawal outcomes. The

post-withdrawal part of each pattern-specific distribution will be modelled using MAR and Copy Reference (CR) approaches. The MI will be carried out in the following steps:

1. Fit a Bayesian negative binomial model with a non-informative prior to the observed data with same set of covariates as in the primary analysis and obtain the posterior distributions of the event rate for both treatment arms.
2. Draw 100 independent samples from the conditional distribution of missing counts given the observed count and period of each patient with missing data based on different post-withdrawal imputation models, described below, for the treatment arms. The conditional distribution is also negative binomial.
3. The observed counts and imputed counts for each patient with missing data are summed.

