4. Each 100 imputed datasets will then be analyzed using the same negative binomial regression model. Estimates from the model such as least squares means and standard errors are then combined across imputation datasets using Rubin's formula, as implemented in the MIANALYZE procedure. These and their 95% confidence interval limits are then exponentiated to obtain the estimate of ABR for each arm and the estimate of the ABR ratio and associated p-value.

MAR and CR approaches are described below:

1. Missing at Random (MAR) Approach: Post-withdrawal missing bleeding events in both fitusiran arm and on-demand arm will be imputed under the randomized arm.
2. Copy Reference (CR) Approach: The expected ABR for a patient in the fitusiran arm both pre- and post-withdrawal is assumed to be the same as that in the on-demand arm. This accounts for a gradual loss of fitusiran effectiveness post-withdrawal. If a patient in fitusiran arm has more events pre-withdrawal than expected if this patient had been in the on-demand arm, then this 'positive residual' will feed through into a higher than expected ABR in the post-withdrawal period. This is because this patient's earlier observed ABR higher than mean event rate suggests the patient has a higher propensity to have events. Post-withdrawal data in the on-demand arm are imputed under randomized arm (assumes MAR approach).

The efficacy analysis based on treatment policy strategy may serve as sensitivity analyses for the primary efficacy analysis based on on-treatment strategy. It is important to note that the estimand based on on-treatment strategy (the primary efficacy analysis) is considered most relevant and applicable in assessing and reporting clinical efficacy of fitusiran vs. on demand treatment.

Per-protocol analysis

Efficacy analysis will be repeated on the per-protocol analysis set as defined in [Section 4](#).

Zero-inflated negative binomial model

To address the concern of potential excessive zero bleeding events, the above on-treatment and treatment policy efficacy analyses will be repeated using the zero-inflated negative binomial model and the results will be presented if model converges.

Covid-19 related sensitivity analysis

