6.3.2.4 Haem-A-QoL

The Haem-A-QoL will be provided to patients ≥17 years of age, and includes 46 items contributing to 10 QoL domains (physical health, feelings, view of yourself, sports and leisure, work and school, dealing with hemophilia, treatment, future, family planning, partnership and sexuality). Scoring for each item is based on a 5-point Likert scale (never, rarely, sometimes, often, and all the time), and higher scores represent greater impairment. The change from baseline in physical health score and total score of Haem-A-QoL at the end of the study will be analyzed using an analysis of covariance (ANCOVA) model with fixed effects of treatment arm and the randomization strata of number of bleeding episodes in the 6 months prior to study entry (≤10 vs >10), baseline Haem-A-QoL physical health score and total score, as covariates. Least square means of the physical health score and total score in each treatment arm and the difference of the least square means of the physical health score and total score in the two arms (along with the 95% CI and p-value) will be presented. The normality assumption based on ANCOVA model will be examined and a sensitivity analysis based on the non-parametric Wilcoxon-Mann-Whitney test will be performed. Domain scores, standardized scale scores, and transformed scale scores for Haem-A-QoL and their changes from baseline will be summarized. The above ANCOVA analysis is based on observed data. For patient with missing assessment due to early withdrawal, a sensitivity analysis will also be performed by imputing the domain score and total score as the worst score if the reason of withdrawal is treatment-related in the corresponding treatment arm, and as the average score for other reasons of withdrawal that are not treatment related in the corresponding treatment arm. The same analysis as main will be performed as a sensitivity analysis by excluding values of those who completed Haem-A-QoL at baseline after first dose of fitusiran.

To evaluate the impact of Covid-19, the same ANCOVA model will also be repeated on Covid-19 unaffected set. In addition, a sensitivity analysis using same ANCOVA model will be performed excluding the data impacted by Covid-19 major/critical protocol deviation. A supportive analysis will be repeated on the patients whose responses level to EQ-5D dimensions “anxiety/depression” is no change or improved from baseline.

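### The Haem-A-QoL withdrawal sensitivity analysis fills some missing scores with a fixed arm average, so that part carries no imputation uncertainty (minor)

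*SAP*

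**What the plan says.** SAP 6.3.2.4 analyses change from baseline to end of study in the physical health and total scores by ANCOVA, with arm, bleeding stratum and baseline score in the model. On missing data it states: "The above ANCOVA analysis is based on observed data". For patients without an assessment because they left early, it adds one sensitivity analysis. It has two parts. The first is a penalty: "imputing the domain score and total score as the worst score if the reason of withdrawal is treatment-related in the corresponding treatment arm". The second part covers all remaining early leavers, whose missing score is set "as the average score for other reasons of withdrawal that are not treatment related in the corresponding treatment arm". The direction of the scale is given ("higher scores represent greater impairment"). No random draw, multiple imputation (MI) or variance correction goes with the rule.

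The other supporting analyses in that section cover the Wilcoxon test, baseline forms completed after the first dose, Covid-19, and the EQ-5D anxiety/depression subset. None of them imputes scores lost to withdrawal.

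Both scores are formally tested at step 5 of the hierarchy. In SAP 5.7 "change in Haem-A-QOL physical health score in the treatment period will be tested first", and the total score follows.

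For bleeding counts, SAP 6.3.1.2 takes a different route. It begins with "Fit a Bayesian negative binomial model with a non-informative prior to the observed data with same set of covariates", draws 100 imputations and pools them by Rubin's formula. Under missing at random (MAR), "Post-withdrawal missing bleeding events in both fitusiran arm and on-demand arm will be imputed under the randomized arm". Under Copy Reference, the expected rate of a fitusiran patient "is assumed to be the same as that in the on-demand arm".

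Protocol Table 1, footnote s, says that the questionnaires are not collected at the early termination visit. A patient who leaves early therefore contributes only a baseline score.

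**The concern.** Giving several patients the same arm average and then analysing them as observed adds degrees of freedom and sample size, but no information. The filled values sit at the centre of their arm, so the residual variance shrinks and the standard error is too small. The rule is the only planned check on whether the two tested Haem-A-QoL results survive scores missing through withdrawal. At stake is whether its confidence interval can be read at face value. For the patients filled with the arm average, that part largely repeats the observed-data estimate with error bars that are wrong.

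**Working it through.** **The plan's own figure.** The only design figure that bears on the amount of missing data is the 20% drop-out allowance in SAP 5.1, made for the annualized bleeding rate. 42/(1 - 0.20) = 52.5. By arm, 14/0.8 = 17.5, rounded to 18, and 28/0.8 = 35, giving 53; at 2:1, 18 + 36 = 54. The planned 54 reproduces. No sample size, SD or power is given for Haem-A-QoL.

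**Inputs.**
- From the documents: 54 patients including about 5 adolescents (Protocol 4.3), 2:1 allocation, and the questionnaire given from age 17. Taking 54 - 5 = 49 patients gives a 16/33 split.
- Assumed: SD 20, mean 45, scale 0-100, baseline correlation 0.3-0.8, missing completely at random.
- Missing patients (on-demand + fitusiran): 2 + 3 at 10%, and 3 + 7 at 20%. The 20% is an upper-range case, because Protocol 5.3.1 and 5.3.2 ask patients who stop dosing to stay for assessments.

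**Closed form, no covariates, every missing score set to its arm average.** The residual sum of squares does not change, so

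SE ratio (filled / observed) = sqrt(df_obs/df_all) × sqrt[(1/16 + 1/33) / (1/n0 + 1/n1)],

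where n0 and n1 are the observed numbers per arm and df_all = 49 - 2 = 47.
- 10% missing (14/30 observed, df 42): sqrt(42/47) × sqrt(0.0928/0.1048) = 0.945 × 0.941 = 0.89.
- 20% missing (13/26 observed, df 37): sqrt(37/47) × sqrt(0.0928/0.1154) = 0.887 × 0.897 = 0.80.

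**Simulation of the ANCOVA (arm, stratum, baseline), no treatment-related withdrawals.**

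| Missing | CI width / observed-data width | Coverage of nominal 95% CI |
|---|---|---|
| 10% | 0.89-0.96 | 92-93% |
| 20% | 0.79-0.92 | 87-89% |

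The estimate moves by about 0.1 points or less on average. A separate run with 36/18 patients and correlation 0.5 agrees. At 20% missing the mean model SE is 0.232 SD units against a true spread of 0.295, and 1 - 0.232/0.295 = 21% too small. The two-sided error of that sensitivity test is then 0.116 (0.081 at 10% missing, 0.062 at 5%), against about 0.046-0.049 for the observed-data ANCOVA.

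**With the worst-score part active (no true effect), CI width relative to observed data.**
- 10% missing, 1 of 3 fitusiran withdrawals penalised: 0.94-1.07 if worst observed in the arm, 0.97-1.15 if scale maximum.
- 20% missing, 2 of 7 penalised: 0.88-1.09 and 0.95-1.24.

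**MI for comparison.** Fitted within arm, the width is 1.04 at 10% and 1.06-1.07 at 20%, with 94-97% coverage. With one baseline slope common to both arms it is 1.01 and 1.02.

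**How often a significant main result stays significant (assumed true effect 10-15 points, 20% missing).**

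| Rule | All correlations | Correlation 0.8 |
|---|---|---|
| Arm average | 88-100% | 88-96% |
| Within-arm MI | 82-97% | 89-97% |
| Common-slope MI | 95-99% | 96-99% |

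The ordering changes because the arm average ignores the patient's baseline. At high correlation this makes the estimate itself noisier: at correlation 0.7 in the 36/18 run, its spread is 0.260 against 0.237 for observed data.

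**The case against.** The strongest reply is that nothing confirmatory depends on this rule. It is a sensitivity analysis of a secondary endpoint at step 5, and no decision is attached to it. That stands, and it is why the point is minor.

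A second reply is that the proposed MI is hardly a new test. With one post-baseline assessment and only baseline score and stratum as predictors, it rests on the same MAR assumption as the main ANCOVA, and its interval is only 1.01-1.07 of the observed-data width. That also stands. MI corrects the error bars; the stress comes from the worst-score penalty, which the SAP already has.

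A third reply is that the magnitudes rest on inputs the documents do not give, including the score range and the split of withdrawals by reason. This is true. The direction of the error for the arm-average rows does not depend on them, but its size does.

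A reader might infer that the arm-average fill makes a positive result easier to confirm. The figures do not support that as a general statement: at correlation 0.8 and 20% missing it is stricter than common-slope MI. A reader might also infer that the interval of the whole rule is always too narrow. Once worst scores enter, it can be wider than the observed-data interval.

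Finally, one might call the worst score undefined. The direction is stated, and the reference to the treatment arm makes the worst score observed in that arm the more natural reading, since a scale maximum would not differ by arm. The phrase could attach to the reason for withdrawal instead, so a clarifying line is useful, but this is a matter of wording.

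**Conclusion.** The point holds and is minor. As written, the arm-average part of the SAP 6.3.2.4 rule treats imputed scores as data and understates the standard error for that component. Nothing elsewhere in the SAP corrects it. If all withdrawals are unrelated to treatment, the interval is roughly 4-11% too narrow relative to the observed-data interval at 10% missing and 8-21% at 20%, on the assumed inputs listed above. With a mix of reasons the net direction is not fixed.

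The error figures of 0.081 and 0.116 might be read as inflation of the trial's type I error. The documents do not support that: the tested ANCOVA uses observed data, and the hierarchy and familywise error rate are unaffected.

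**What to change.** In SAP 6.3.2.4, replace the arm-average fill by MI of the end-of-study score for withdrawals that are not treatment-related. Use normal regression on baseline score and stratum, by arm, pooled by Rubin's rules with a small-sample degrees-of-freedom adjustment. State whether the baseline slope is arm-specific or common. The 100 imputations of SAP 6.3.1.2 can be kept, but its negative binomial count model cannot be reused for a score. Keep the worst-score penalty as the stress component.

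Two optional additions:
- One line saying whether the worst score is the worst observed in that arm or the scale maximum.
- A reference-based version that imputes fitusiran withdrawals from the on-demand model, labelled a conservative stress test. Its coverage is 97-99% when there is no effect, and at 20% missing with a true effect of 10-15 points a significant result survives in only 33-75% of trials. This is a choice of stress test and corrects no error.

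The cost is SAP wording and a little programming, with no protocol amendment. The sensitivity interval becomes about 1.01-1.07 of the observed-data width where no withdrawal is penalised. The MI shares the main analysis's MAR assumption and should be described that way.

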- q All patients will be tested for antibodies to fitusiran at the Screening visit. After randomization, testing for antibodies to fitusiran will be performed in the fitusiran treatment arm only.
- r Blood samples for PK analysis will be collected at the time points listed in Table 7 in all fitusiran arm patients. In East Asian patients in the fitusiran arm at East Asian sites, blood samples for PK analysis will be collected at the time points listed in Table 8 (which includes all those time points listed in Table 7), and pooled urine samples will be collected for PK analysis at the time points listed in Table 9.
- s Must be completed at the clinic. Will be collected at EOS visit; not collected at ET visit.
- t Will include review of entries, (symptoms of bleed events, bleed causality, bleed severity, doses administered), whether appropriate site contact occurred regarding treatment of bleeds, and review of patient bleed management plan and recommendations and requirements for site contact regarding dosing.
- u It is strongly preferred that BPA administration and bleeding events are entered in the eDiary immediately or within 24 hours. Additional patient follow-up may be required as described in Section 7.2.1. Patients in the fitusiran treatment arm who present in the clinic with symptoms characteristic of a potential bleeding episode should have assessments completed per Table 2.
- v Perioperative assessment safety and hemostatic efficacy only in patients undergoing operative procedures while on study (see Table 10).
- w AEs will be monitored and recorded from date of signed informed consent through Follow-Up. Signs and symptoms of thrombosis will be evaluated at every visit (see Section 6.5)
- x In addition to recording concomitant medications, documented history of prior medications will be collected during Screening.

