3	This version	To update Per-protocol Analysis Set definition	The detail deviations are included in the Per-protocol analysis set definition in Section 4.
3	This version	To define Covid-19 Unaffected Set	Covid-19 Unaffected Set is defined in Section 4.
3	This version	To clarify baseline definition for fitusiran group	For fitusiran group only, baseline definition is changed from Day 1 to first dose date in Section 5.5
3	This version	To clarify the multiplicity adjustment for Haem-A-QOL endpoints	For the two Haem-A-QOL scores (physical health score and total score), physical score will be tested first followed by total score.
3	This version	To add patient disposition category for Covid-19 impact summary	Patients discontinue the treatment due to Covid-19 and patient discontinue the study due to Covid-19 are added in Section 6.1
3	This version	Due to the exclusion criteria 6, the analysis of fibroscan/fibrotest result at baseline against worst post-baseline ALT elevation is not necessary	The related analysis is removed in Section 6.6.3

SAP version number	Date approved	Rationale	Description of statistical changes
3	This version	To add the efficacy analyses for ABR endpoints due to Covid-19 impact	For ABR, the sensitivity analyses on Covid-19 unaffected set is added in Section 6.3. In addition, a sensitivity analysis to exclude the bleeds during the period of missing at least 2 consecutive doses due to Covid-19 event is added in Section 6.3.
3	This version	To add the analyses for Haem-A-QoL due to Covid-19 impact	For sensitivity analyses, ANCOVA model will be run on Covid-19 unaffected set, on the set excluding data collected with Covid-19 impact, on the set of patients whose responses level to EQ-5D dimensions “anxiety/depression” is no change or improved from baseline.
3	This version	To add the sensitivity analysis for Haem-A-QoL baseline assessments	For sensitivity analyses, the same analysis as main but excluding values of those who completed Haem-A-QoL at baseline on the same day but after first dose of fitusiran.
3	This version	To add the AE summary related to Covid-19 infection	AE potentially consistent with COVID-19 will be summarized by SOC and PT and list will also be provided. The search term list is added in the Appendix 8.2
3	This version	To add AE summary by hemophilia type	By hemophilia type summary is added to key AE tables.

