3.2 Endpoints

3.2.1 Efficacy Endpoints

Primary and secondary endpoints for Global and US protocols are in the table below.

	Global Protocol	US Protocol
Primary	Annualized Bleeding Rate (ABR) in the efficacy period	ABR in the treatment period
Secondary	ABR in the treatment period	ABR in the efficacy period
	Annualized spontaneous bleeding rate in the efficacy period	
	Annualized joint bleeding rate in the efficacy period	
	Change in Haem-A-QOL physical health score and total score in the treatment period	
	ABR in the onset period	

Exploratory Efficacy Endpoints

- Change in the following in the treatment period:
 - Treatment Satisfaction Questionnaire for Medication (TSQM) domain scores
 - Haemophilia Activities List (HAL) score
 - Paediatric HAL (pedHAL) score
 - EuroQOL-5 dimension (EQ-5D) score
 - Haemo-QOL score
 - Hemophilia Joint Health Score (HJHS)
- Number of target joint bleeding episodes
- Annualized weight-adjusted consumption of bypassing agents
- Change in patient resource use (eg, work/school attendance, visits to doctor/hospital)

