8.1.4 EuroQol-5 dimension 5 level (EQ-5D-5L) score

The EQ-5D-5L is a standardized instrument for use as a measure of QoL outcome. It consists of a descriptive system and a visual analog scale (VAS).

- 1) EQ-5D descriptive system: has 5 dimensions (mobility, self-care, usual activities, pain/discomfort, anxiety/depression) with 5 levels (no problems, slight problems, moderate problems, severe problems, and extreme problems).

- 2) EQ-5D VAS: is a continuous score ranging from 0 to 100.
- 3) EQ-5D Valuation index: The information of the 5 dimensions of the descriptive system summarized into one index. The EQ-5D-5L index value is calculated using the crosswalk link function and the individual responses to the EQ-5D5L descriptive system. If any of the 5 dimensions have missing values at a given time point, the index value will not be computed.

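### The supportive Haem-A-QoL analysis selects patients on EQ-5D anxiety/depression change at the outcome visit, so it can be biased and cannot isolate Covid-19

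*SAP*

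**What the plan says.** The main Haem-A-QoL analysis in SAP 6.3.2.4 is an ANCOVA of "The change from baseline in physical health score and total score of Haem-A-QoL at the end of the study", on observed data, with treatment arm, bleeding stratum and baseline scores in the model.

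The paragraph on Covid-19 in the same section adds three analyses: the ANCOVA on the Covid-19 Unaffected Set, the ANCOVA without data affected by major or critical Covid-19 deviations, and a third described as "A supportive analysis will be repeated on the patients whose responses level to EQ-5D dimensions" anxiety/depression "is no change or improved from baseline". The version 3 entries in SAP 2.6 list it with the Covid-19 sensitivity analyses: "on the set of patients whose responses level to EQ-5D dimensions". Patients who worsened on that item are left out, whatever the cause.

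The SAP names no visit for the filter. Protocol Table 1 marks EQ-5D and Haem-A-QoL at Day 1 and at the EOS/ET column only, and footnote s says of both: "Will be collected at EOS visit; not collected at ET visit". EOS is therefore the only scheduled post-baseline EQ-5D.

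SAP 3.2.1 lists change in "EuroQOL-5 dimension (EQ-5D) score" as an exploratory efficacy endpoint. SAP 8.1.4 says the EQ-5D descriptive system "has 5 dimensions (mobility, self-care, usual activities, pain/discomfort, anxiety/depression) with 5 levels". The Haem-A-QoL domains include "physical health, feelings, view of yourself, sports and leisure, work and school, dealing with hemophilia, treatment, future".

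**The concern.** Membership of the analysis set depends on a patient-reported result obtained after randomisation, in an open-label trial, at the same visit as the outcome. The plan itself treats that result as something fitusiran may change. If fitusiran improves mood, more on-demand than fitusiran patients are removed. If mood change and Haem-A-QoL change also move together within an arm, those removed tend to have the poorer Haem-A-QoL changes. The patients left are then no longer comparable by randomisation.

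The filter is also not specific to Covid-19. Nothing limits it to worsening attributed to the pandemic; bleeding or pain could worsen the item too, and bleeding is what the drug is meant to reduce.

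For the total score there is an added concern: domains such as feelings, view of yourself and future overlap in content with an anxiety/depression item. This does not apply to the physical health score.

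What is at stake is interpretation. A smaller effect in the filtered set could reflect Covid-19 or the filter, and an unchanged effect would not establish robustness to Covid-19.

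**Working it through.** **Plan figures.** The documents give no effect size, SD or power for Haem-A-QoL, so there is no stated figure for this analysis to reproduce. SAP 5.1 plans 14 on-demand and 28 fitusiran evaluable patients. The total follows: 14 / 0.80 = 17.5, rounded up to 18; at 2:1, 18 + 36 = 54.

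**Assumed inputs (not in the documents).**
- True Haem-A-QoL effect: 0.60 SD of change, stated as benefit.
- On-demand patients who worsen on anxiety/depression: 20%.
- Fitusiran improves anxiety/depression by d = 0, 0.3 or 0.6 SD.
- Within-arm correlation r between the two changes: 0.3 to 0.7.
- Both changes bivariate normal with unit SD.

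**Formula.** Let c be the worsening cut-off, with Φ(c) = 0.80, so c = 0.842. Patients at or below c are kept. In on-demand patients the mean anxiety change among those kept is shifted by −λ₀, where λ₀ = φ(c)/Φ(c). In fitusiran patients the cut-off sits at c + d from their own mean, so the shift is −λ₁, where λ₁ = φ(c + d)/Φ(c + d). A fraction r of each shift carries over to Haem-A-QoL, so:

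filtered effect = 0.60 − r(λ₀ − λ₁)

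λ₀ = 0.280/0.800 = 0.350.

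| d | Fitusiran removed | λ₁ | λ₀ − λ₁ | Filtered effect, r = 0.3 | Filtered effect, r = 0.7 |
|---|---|---|---|---|---|
| 0 | 20.0% | 0.350 | 0 | 0.60 | 0.60 |
| 0.3 | 12.7% | 0.208/0.873 = 0.238 | 0.112 | 0.566 | 0.522 |
| 0.6 | 7.5% | 0.141/0.925 = 0.153 | 0.197 | 0.541 | 0.462 |

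The effect is therefore 0.034 to 0.138 SD too small, which is 6% to 23% of 0.60. It is not distorted when d = 0, nor when r = 0.

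**Second check, closer to the SAP model.** A simulation of 1.5 million patients at 2:1 fitted an ANCOVA of change on arm and baseline, with a five-level anxiety/depression item and the filter of end level no worse than baseline level. Assumptions: correlation between the two baseline measures 0.4, baseline-to-end slope 0.6, effect on latent anxiety/depression 0, −0.3 or −0.6 SD, residual correlation 0, 0.3 or 0.6. Negative values favour fitusiran.

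| Anxiety effect | Kept, fitusiran vs on-demand | Shift, correlation 0.3 | Shift, correlation 0.6 |
|---|---|---|---|
| 0 | 75% vs 75% | 0.00 | 0.00 |
| −0.3 | 85% vs 75% | +0.03 | about +0.065 |
| −0.6 | 91% vs 75% | about +0.06 | +0.11 |

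With a true effect of −0.50 SD the all-patient ANCOVA returned −0.50. Where the shift was non-zero, the filtered one returned −0.47 to −0.39. With zero residual correlation the shift was zero within simulation error.

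**On the trial's scale.** The standard error of an unadjusted difference with 14 and 28 patients is √(1/14 + 1/28) = 0.33 SD. It is somewhat larger once patients under 17, who do not complete Haem-A-QoL, are left out; baseline adjustment would reduce it. The shift is 0.034/0.33 to 0.138/0.33, or about 0.1 to 0.4 standard errors. Expected removals are 0.20 × 14 = 2.8 on-demand patients and 0.075 × 28 = 2.1 to 0.127 × 28 = 3.6 fitusiran patients. Removing 3 and 3 at random would by itself move the estimate with an SD of √(1/11 − 1/14 + 1/25 − 1/28) = 0.15.

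**The case against.** The strongest reply is that nothing confirmatory depends on this analysis. The SAP calls it supportive, SAP 5.7 tests only the main Haem-A-QoL comparisons, the main ANCOVA does not use the filter, and two other Covid-19 analyses stand beside it. That is correct. A reader might infer that the confirmatory Haem-A-QoL result or the familywise error rate is compromised; the documents do not support that.

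A reader might also infer that the filter necessarily biases the comparison. It does not. Bias needs both a drug effect on anxiety/depression and a residual correlation with Haem-A-QoL. Listing EQ-5D as an endpoint and expecting better quality of life make both plausible, but the documents quantify neither.

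The direction and size also count against a stronger claim. If fitusiran improves mood, the shift runs against fitusiran, so in that case it does not create false support. The sign would be expected to reverse if the drug worsened mood, which was not simulated. In the assumed range the shift is no larger than the movement that random removal of as many patients would cause. The SAP sets no rule for reading a smaller effect as Covid-19 influence.

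The content-overlap argument reaches only the total score; the physical health score, tested first, is outside it.

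What remains is that a robustness check should have an interpretable result. This one is selected after randomisation, on an efficacy variable, with no link to Covid-19, and neither its supportive label nor the small expected shift cures that.

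**Conclusion.** The concern holds as a minor point. The filter selects on a post-randomisation efficacy endpoint judged at the outcome visit, and it can bias the Haem-A-QoL comparison. That the visit is EOS follows from Table 1, since the SAP does not say so. Under the assumed inputs a true effect of 0.60 SD would appear as about 0.57 to 0.46 SD, with 7.5% to 12.7% of fitusiran against 20% of on-demand patients removed. There is no bias if fitusiran does not affect anxiety/depression. The shift is at most about 0.4 of a standard error of roughly 0.33 SD.

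The primary estimate, the main Haem-A-QoL test and error control are unaffected. The practical consequence is confined to interpretation: the analysis cannot tell Covid-19 influence from a selection artefact.

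**What to change.** Do not use the EQ-5D change filter as a Covid-19 robustness analysis; remove it from SAP 6.3.2.4 and update the entry in SAP 2.6.

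If a Covid-19 split is wanted, keep all observed patients and classify them by something treatment cannot alter: whether the scheduled EOS date, counted from the randomisation or Day 1 date, falls before or after a prespecified pandemic start date. Run the same ANCOVA in each part, optionally with baseline anxiety/depression level as a covariate, and present estimates with confidence intervals.

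If the filtered analysis is kept, label it descriptive and report the number excluded by arm. The other two Covid-19 analyses can stay, but note that the Covid-19 Unaffected Set in SAP 4 is also defined by events after randomisation.

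The cost is SAP wording and the choice of a pandemic start date, which the documents do not give. No new patient data are needed. The drawbacks are that some date strata may be small in a trial of 54, that calendar time is only a proxy for Covid-19 exposure, and that the questionnaire still exists only for patients who reach EOS.
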